8.3.2 Efficacy assessment 2

Expanded Disability Status Scale (EDSS).

The EDSS is an ordinal scale used for assessing neurologic impairment in MS based on a neurological examination. It consists of scores in each of seven functional systems (FSs) that are then combined to determine the EDSS steps [ranging from 0 (normal) to 10 (death due to MS)]. The FSs are Visual, Brain Stem, Pyramidal, Cerebellar, Sensory, Bowel & Bladder, and Cerebral functions. The FSs and EDSS steps will be assessed in a standardized manner. EDSS is a widely used and accepted instrument to evaluate disability status at a given time and, longitudinally, to assess disability progression in clinical studies in MS.

[REDACTED] EDSS assessments obtained on an unscheduled visit can only be used to mark the onset of a possible sustained progression.

Patient who dies due to MS will be counted as progression. A patient who misses one or more scheduled visits that are preceded [REDACTED]

MRI parameters: T1 hypo-intense lesion number and volume; T2 lesion volume, new/newly enlarged T2 lesion number; Gd- enhancing T1 lesion number and volume;

All participants will undergo MRI scanning of the brain in accordance with the study Imaging Acquisition Guidelines during the Screening visit (up to 30 days prior to day 1), provided the participant meets all other I/E criteria, and then for the Month 12 and Month 24 visits. Each MRI scan performed for the study needs to be centrally reviewed by a neuro-radiologist from the sponsor designated imaging vendor as part of the efficacy analysis. Each site investigator will be responsible to have a qualified neuro-radiologist review each MRI scan to determine if there may be any incidental findings unrelated to the planned observations within the study protocol detected on the images. Refer to [Section 16.7](#) Appendix 7 for Guidance on Safety monitoring.

Participant suspected MS relapse could undergo additional MRI scan on his/her own account in alignment with the investigator. To avoid potential interference caused by steroids used for the treatment of MS relapses, the following restrictions will be applied for this study:

- In case of relapse, if an MRI would have been scheduled within 30 days of the initiation of steroid treatment, this MRI should be performed before steroid treatment is initiated.
- No MRI scan should be performed while a participant is on intravenous steroid therapy and within 30 days after termination of steroid therapy.

Scanning

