2.1.2 Visit windows

2.1.2.1 Visit windows for treatment period

Visit-windows will be used for both efficacy and safety data summaries by visit. Visit windows define a time period “around” the targeted visit date as defined in the evaluation schedule of the clinical study protocol. Visit-windows are non-overlapping and defined without gaps between

consecutive visit windows. The width of visit windows may vary over the course of the study period.

Baseline assessments are defined in [Section 2.1.1](#) and do not require a visit window.

The purpose of visit windows is to analyze data based on the actual study days (rather than "nominal" visits). E.g. if a subject's Month 1 visit is delayed; it is possible that the Month 1 data be re-aligned to visit-window Month 2 and be summarized under Month 2.

- For **efficacy analyses** all nominal visits (i.e. excluding unscheduled visits) will be mapped into one of the defined visit-windows.

-For **safety analyses** all visits (scheduled and unscheduled) will be mapped to visit windows. Safety data from unscheduled visits may be reported separately if applicable.

It is possible that more than one assessment of a subject fall into a particular visit-window. [Section 2.1.2.3](#) deals with the statistical approaches to handle multiple visits in a given visit-window.

Tables displaying summary statistics "by visit" will also use the term *visit-window* as column header; this is to remind the reviewer that multiple assessments of a subject might be summarized. Below tables provide visit-windows definitions for applicable parameters.

Table 2-3 Visit-windows for MRI

Visit-window	Start day	Target Day	End day
Month 12	1	360	540
Month 24	541	720	900

Table 2-4 Visit-windows for routine laboratory values

Visit-window	Start day	Target Day	End day
Month 1	1	30	60
Month 3	61	90	135
Month 6	136	180	225
Month 9	226	270	315
Month 12	316	360	450
Month 18	451	540	630
Month 24	631	720	810

Table 2-5 Visit-windows for vital signs*

Visit-window	Start day	Target Day	End day
Month 1	1	30	60
Month 3	61	90	135
Month 6	136	180	225
Month 9	226	270	315
Month 12	316	360	405
Month 15	406	450	495
Month 18	496	540	585
Month 21	586	630	675
Month 24	676	720	765

*Data collected from Day 1 protocol scheduled visit will not be mapped to the visit windows due to different data collection on those visits.

Table 2-6 Visit-windows for Electrocardiogram (ECG)

Visit-window	Start day	Target Day	End day
Month 1	1	30	60
Month 3	61	90	135

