2.7.1 Secondary endpoints

Secondary efficacy endpoints include:

- To estimate annualized rate of new or newly enlarged T2 lesions, below variables will be derived:
 - The total number of new or newly enlarged T2 lesions within 30 days from the last dose date will be derived by taking the sum of number of new or newly enlarged T2 lesions from all scheduled MRI scans (as compared to the previous scan) with a non-missing value within 30 days from the last dose date.
 - The time (in years) from screening scan will be calculated as (date of last scheduled MRI scan with a non-missing value for the number of new or enlarging T2 lesions within 30 days from the last dose date – date of screening scan +1)/365.25.
- Volume of T2 lesions.
- To estimate the number of Gd-enhancing T1 lesions per scan, below variables will be derived:
 - The total number of Gd-enhancing T1 lesions within 30 days from the last dose date will be derived by taking the sum of number of Gd-enhancing T1 lesions from the all scheduled MRI scan with a non-missing value within 30 days from the last dose date. Any Gd-enhanced T1 data obtained less than 30 days after the termination of steroid therapy which is used to treat MS relapses will not be included in analysis of Gd-enhancing T1 lesion related endpoint.
 - The number of MRI scans will be derived by counting the number of scheduled MRI scans with non-missing values for the number of Gd-enhancing T1 lesions within 30 days from the last dose date (i.e. the number of scans contributed to the derivation of the above variable: the total number of Gd-enhancing T1 lesions within 30 days from the last dose date).
- Volume of Gd-enhancing T1 lesions.
- Number of T1 hypo-intense lesions.
- Volume of T1 hypo-intense lesions.

Change and % change in volume of T2 lesions, Gd-enhancing T1 lesions and T1 hypo-intense lesions from baseline will only be defined for subjects with both baseline and post-baseline values and will be calculated as:

change from baseline = post-baseline value – baseline value;

% change from baseline = change from baseline / baseline value*100.

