2.7.2 Statistical hypothesis, model, and method of analysis

Methods of analyses for efficacy endpoints defined in [Section 2.7.1](#) are described below.

- The annualized rate of new or newly enlarged T2 lesions for Adult group will be estimated by a negative binomial regression model with log-link function, the total number of new or newly enlarged T2 lesions within 30 days from the last dose date (per subject) as the response variable. Natural log of time from screening scan in years will be used as the offset. The model will include baseline age and baseline volume of T2 lesions as continuous covariates. The estimated number of new or newly enlarged T2 lesions will be obtained together with the corresponding 95% confidence interval.

Supportive analyses: similar analyses may also be conducted to obtain the estimated annualized rate of new or newly enlarged T2 lesions at month 0 to month 12 and at month 12 to month 24 for Adult group.

Descriptive summary statistics (mean, median, standard deviation, min, max) for the number of new or newly enlarged T2 lesions will be provided by age group and by visit. Number and percentage of subjects free of new or newly enlarged T2 lesions will also be provided by age group.

- The number of Gd-enhancing T1 lesions per scan for Adult group will be estimated by a negative binomial regression model with log-link function, the total number of Gd-enhancing T1 lesions within 30 days from the last dose date (per subject) as the response variable. Natural log of the number of MRI scans will be used as the offset. The model will include baseline age and number of Gd-enhancing T1 lesions at baseline as continuous covariates. The estimated number of Gd-enhancing T1 lesions per scan will be obtained together with the corresponding 95% confidence interval.

Supportive analyses: descriptive summary statistics (mean, median, standard deviation, min, max) for the number of Gd-enhancing T1 lesions will be provided by age group and by visit. Number and percentage of subjects free of Gd-enhancing T1 lesions will also be provided by age group.

- Descriptive summary statistics (mean, median, standard deviation, min, max) will be provided by age group and by visit for the following: volume of T2 lesions, volume of Gd-enhancing T1 lesions, number of T1 hypo-intense lesions, volume of T1 hypo-intense lesions, change and % change in volume of T2 lesions, Gd-enhancing T1 lesions and T1 hypo-intense lesions from baseline.

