2.7.3 Handling of missing values/censoring/discontinuations

As a general rule, missing data will not be imputed in any secondary endpoint analyses. For MRI parameters, only assessments taken within 30 days from the last dose date will be included in the analysis.

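### The by-visit Month 24 summary of new or newly enlarged T2 lesions can mix counts over about one year with counts over about two, because the comparator scan plays no part in the visit-window.

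*SAP*

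**What the plan says.** - **Scans.** Protocol 8.3.2 schedules brain MRI at Screening "and then for the Month 12 and Month 24 visits". Table 8-1 adds scans at EOT and EOS for participants who stop early.
- **What is counted.** SAP 2.7.1 builds the T2 total from the counts "from all scheduled MRI scans (as compared to the previous scan) with a non-missing value within 30 days from the last dose date". Each scan's value is thus a count over the interval since its comparator.
- **How it is tabulated.** SAP 2.7.2 states that descriptive statistics "for the number of new or newly enlarged T2 lesions will be provided by age group and by visit". No time scaling and no condition on the comparator is given.
- **What a visit is.** SAP 2.1.2.1 says "Visit-windows will be used for both efficacy and safety data summaries by visit". In Table 2-3, Month 12 is days 1–540 (target 360) and Month 24 is days 541–900 (target 720). For efficacy, all nominal visits are mapped, and Table 2-1 includes EOT and EOS among these.
- **Missing data.** SAP 2.7.3 says "As a general rule, missing data will not be imputed in any secondary endpoint analyses" and keeps only scans within 30 days of the last dose. SAP 2.1.2.3 deals with several assessments in one window, not with an absent earlier one.
- **Model-based rate.** The main T2 model in SAP 2.7.2 uses log years since the screening scan as offset. Similar models for months 0–12 and 12–24 are optional, and their offset and comparator are not defined.

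**The concern.** An interval count has a meaning only together with the length of its interval. The main T2 model respects this through its offset; the by-visit table does not. If the Month 12 scan was not done or could not be used, the scan before Month 24 is the screening scan. The Month 24 value then covers both years but sits under the same heading as other participants' second-year counts.

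New/newly enlarged T2 lesion number is a named secondary endpoint, and readers will naturally take the Month 24 column as the second-year result. Protocol 12.5 also asks for the number and proportion of patients with new or newly enlarged T2 lesions at 12 and 24 months, again without stating the comparator. The optional month 12–24 rate is exposed in the same way if it is built from the same per-scan counts with a one-year offset.

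The situation can arise. In SAP 2.8.3 and 2.8.4 the sponsor plans for visits missed because of COVID-19 by using off-site laboratory, ECG and vital-sign data; no equivalent for MRI is visible. Protocol 8.3.2 also bars scans during intravenous steroids and for 30 days after steroid therapy ends, though this will more often delay a scan than remove it.

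**Working it through.** The documents state no T2 lesion rate and no missing-scan rate, so there is no planned figure to reproduce. All rates below are assumptions.

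**Step 1: interval lengths.** Screening can be 1 to 30 days before Day 1 (Protocol Table 8-1); target days come from SAP Table 2-3.
- With a Month 12 comparator: (720 − 360)/365.25 = 0.99 years.
- With a screening comparator: (720 + 1)/365.25 = 1.97 to (720 + 30)/365.25 = 2.05 years.

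**Step 2: effect of a missing Month 12 scan on the Month 24 mean.** Let L1 and L2 be the mean counts in years 1 and 2, and m the share of the Month 24 column without a usable Month 12-window scan. If counts add across scans,

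Month 24 mean = (1 − m) × L2 + m × (L1 + L2) = L2 + m × L1,

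so the relative increase is m × L1/L2.

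| m | L1/L2 = 1 | L1/L2 = 1.5 | L1/L2 = 2 |
|---|---|---|---|
| 0% | 0% | 0% | 0% |
| 5% | 5% | 7.5% | 10% |
| 10% | 10% | 15% | 20% |
| 15% | 15% | 22.5% | 30% |

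A simulation of 400,000 participants (gamma-Poisson counts, assumed dispersion 2, scans missing at random) agrees. With L1 = L2 = 1 and m = 10% the mean goes from 0.998 to 1.098; with L1 = 2, L2 = 1 and m = 10% it goes from 1.000 to 1.201.

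**Step 3: proportion free of new lesions, if shown at Month 24.** For a negative binomial count, P(0) = (1 + kμ)^(−1/k). With k = 2, a one-year mean of 1 gives 3^(−1/2) = 0.577 and a two-year mean of 2 gives 5^(−1/2) = 0.447. At m = 10% the proportion falls by 0.10 × (0.577 − 0.447) = 0.013, or 1.3 percentage points.

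**Step 4: intervals that are too short.** A participant scanned at day 360 with an EOT scan at day 560 contributes 200 days to the Month 24 column. A Month 12 scan as late as day 540 followed by one at day 720 contributes 180 days. At a constant rate, a share s with 200 instead of 360 days lowers the mean by s × (1 − 200/360) = 0.44 × s. With L1 = L2, m = 5% and s = 10%, the net change is 5% − 4.4% = +0.6%. A larger s makes it negative.

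**Step 5: the overall annualized rate.** With a Month 12 scan the total is the year 1 count plus the year 2 count. Without it, the total is the single count back to screening. The offset runs from the screening scan to the last scan in both cases. Under additivity neither numerator nor time changes.

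**Step 6: effect of the restriction.** Keeping only participants with a Month 12 comparator returns L2 if scans are missing at random (simulated 0.998 and 1.001 in the two Step 2 cases). Dividing each count by its interval does not do the same when the years differ: with L1 = 2, L2 = 1 and m = 10%, the result is 0.9 × 1 + 0.1 × 1.5 = 1.05, not 1.

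**The case against.** **The trigger may be rare.** Dropout does not cause it, since scans more than 30 days after the last dose are excluded. Table 2-3 accepts any scheduled scan up to day 540 as Month 12, so a delayed scan normally still counts. What remains is a participant still on drug, or within 30 days of the last dose, at a scan after day 540 with no usable scheduled scan before that. This stands: m is unknown and may be zero.

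**The formula is close to an upper bound.** A lesion that is new in year 1 and enlarges in year 2 is counted twice with two scans but once with one. This stands. The shift is also modest against sampling error: with a mean of 1, dispersion 2 to 4 and 80 participants, the standard error is √((1 + k)/80) = 0.19 to 0.25, while the shift at equal yearly rates is 0.05 to 0.15.

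**The comparator is partly inferred.** The previous-scan wording defines the total for the annualized rate and is not repeated for the by-visit table. Central reading rules are not in the public documents, and the imaging vendor might leave the count missing without a Month 12 scan. However, an offset running from screening to the last scan with a value fits only a count that reaches back to screening. Either way, stating the rule would settle it.

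**The affected outputs are few.** SAP 2.7.2 gives the lesion-free percentage by age group, not expressly by visit. Protocol 12.5 asks for patients with lesions, not a mean count. The month 12–24 model is optional, and the protocol plans no hypothesis tests. All of this stands and limits the point to descriptive and supportive results.

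**Conclusion.** The point holds as a minor one. Followed as written, the SAP lets the Month 24 column combine counts over about one year with counts over about two. Taken alone, a missing Month 12 scan raises the Month 24 mean by up to about m × L1/L2: up to 5–15% for m = 5–15% and equal yearly rates, more if year 1 is the more active year, and nothing if m = 0. These figures rest on assumed m and L1/L2 and on counts adding across scans.

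A reader might infer that the Month 24 figure is always too high, so that improvement from year 1 to year 2 is always understated. The documents do not support that: short intervals from early EOT/EOS scans or late Month 12 scans act the other way, and the net direction depends on the mix. A reader might also infer that the main T2 result or the trial's primary result is biased. Neither is. The annualized T2 rate carries an offset from the screening scan, and the ARR does not use MRI counts.

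**What to change.** In SAP 2.7.2:

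1. Limit the by-visit Month 24 summary of new/newly enlarged T2 lesions, any Month 24 proportion with or free of new lesions, and the month 12–24 supportive model to participants whose comparator scan lies in the Month 12 window.
2. In the interval-specific models, use log years between the two compared scans as the offset.
3. In the table, show the number left out for lack of a Month 12 comparator and the distribution of comparator intervals. The restriction alone does not remove the short intervals, so the reader needs to see them.

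Per-year scaling of each count should not be treated as an equivalent substitute for item 1, since it averages the two years for the affected participants. Moving the limits in Table 2-3 would not help either, because the gap lies in the comparator.

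The cost is a few lines of SAP text and a programming condition. The Month 24 column loses a few participants, and the restriction may select if missed scans are related to relapse or steroid use. Those left out remain in the overall annualized-rate model.

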2.1.2.1.1 Time points for first dose monitoring ECG and Vital signs

The first dose monitoring for Gilenya treatment will be analyzed.

The vital sign values at specified hours as recorded in the database will be used. For the second dose vital signs, data will be summarized similarly.

2.1.2.2 Visit windows after study drug discontinuation

For summaries of data collected after study drug discontinuation, data from both treatment period and safety follow-up period will be considered. All reporting will be done based on visit windows defined relative to the last administration of study drug.

The visit window definitions are provided in [Table 2-7](#) where the Start day and End day are relative to the date of last administration of study drug. For the “Last assessment on drug”, the last assessment with non-missing value taken before or on the date of last administration of study drug will be summarized (no visit window applies). For the “Month 3 after LDD (last dose date)” visit-window, assessments taken at least 1 day after but no more than 135 days after the date of last administration of study drug will be considered. LDD stands for last dose date and will be footnoted in applicable outputs.

Table 2-7 Visit-windows after study drug discontinuation

Visit-window	Start day	Target Day	End day
Last assessment on drug	NA	NA	NA (see above or section 2.1.1)
Month 3 after LDD	2	90	135
Month 6 after LDD	136	180	225
Month 9 after LDD	226	270	315
Month 12 after LDD	316	360	405
Month 15 after LDD	406	450	495
Month 18 after LDD	496	540	585
Month 21 after LDD	586	630	675
Month 24 after LDD	676	720	765
Month 27 after LDD	766	810	855

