Then the participants should come to site and be evaluated month 1 and then every three months till the end of treatment up to 24 months.

Follow Up (2 months): Participants who completed Treatment Period will return for the Follow-up visit 2 months after the last dose of study drug.

Figure 3-1 Study design

4 Rationale

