At the onset of any symptom indicative of a relapse during the study, participants may have unscheduled visits to confirm relapse and collect information. In addition, participants may have unscheduled visits for other reasons, including but not limited to infection, blurred vision. In case of MS relapse, these visits are essential for relapse evaluation and confirmation and have to be carefully documented on the Unscheduled Visit eCRFs. Exams to confirm relapse is based on investigator's discretion. During unscheduled visits for other reasons, information should be collected per Unscheduled Visit eCRFs.

Participants should follow as much as possible the visit schedule with an allowed "visit window" of \pm 3 days for Month 1 and Month 3 visit and \pm 5 days for Month 6, Month 9, Month 12, Month 15, Month 18, Month 21, Month 24 and 2-month follow up visit. In case a visit was performed outside the visit window, subsequent visits should be performed according to the original visit schedule and as applicable per study label guidelines necessary first dose monitoring should be performed at site. In the study, one month is defined as 30 calendar days.

As per Section 4.6, during a public health emergency as declared by local or regional authorities i.e. pandemic, epidemic or natural disaster that limits or prevents on-site study visits, alternative methods of providing continuing care may be implemented by the investigator as the situation dictates. If allowable by a local health authority, national and local regulations and depending on operational capabilities, phone calls, virtual contacts (e.g. tele consultation) or visits by site staff/off-site healthcare professional(s) staff to the participant's home, can replace certain protocol assessments, for the duration of the disruption until it is safe for the participant to visit the site again. If the Investigator delegates tasks to an off-site healthcare professional, the Investigator must ensure the individual(s) is/are qualified and appropriately trained to perform assigned duties. The Investigator must oversee their conduct and remain responsible for the evaluation of the data collected.

Table 8-1 Assessment Schedule

Period	Screening	Treatment Period													Follow-up Visit ²
Visit Name	Screening	Day 1	Month 1	Month 3	Month 6	Month 9	Month 12	Month 15	Month 18	Month 21	Month 24	EOT ³	EOS ⁴	Follow-up Visit	

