9.1 Discontinuation

9.1.1 Discontinuation from study treatment and from study

Discontinuation of study treatment for a participant occurs when study treatment is permanently stopped for any reason (prior to the planned completion of the study drug administration, if any) and can be initiated by either the participant or the investigator.

The investigator must discontinue study treatment for a given participant if, he/she believes that continuation would negatively impact the participant's well-being.

Discontinuation from study treatment is required under the following circumstances:

- Participant/guardian decision
- Pregnancy

- Use of prohibited treatment as per recommendations in the prohibited treatment section
- Any situation in which continued study participation might result in a safety risk to the participant

Take into consideration the following to establish the list of circumstances under which study treatment must be discontinued:

- Adverse events, abnormal laboratory values or abnormal test result that indicate a safety risk to the participant. Refer to [Section 16.7](#) for Guidance for safety monitoring
- Unsatisfactory therapeutic effect
- Participant's condition no longer requires study treatment

If discontinuation from study treatment occurs, the investigator should make a reasonable effort to understand the primary reason for the participant's discontinuation from study treatment and record this information.

Participants who discontinue from study treatment should be asked to agree to **return for the end of treatment (EOT) and follow up visits indicated** in the Assessment Schedule [Table 8-1](#) (refer to section 8).

If the participant cannot or is unwilling to attend any visit(s), the site staff should maintain regular telephone contact with the participant, or with a person pre-designated by the participant. This telephone contact should preferably be done according to the study visit schedule.

After discontinuation from study treatment, at a minimum, in abbreviated visits, the following data should be collected at clinic visits or via telephone/email contact:

- New / concomitant treatments
- Adverse Events / Serious Adverse Events

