2.8.6 Safety evaluation after last administration of study treatment

The SAF will be used for analyses in this section.

Safety data collected after last administration of study treatment includes adverse events, vital signs, routine laboratory parameters and ECG. No safety cutoff date will be applied in the analyses defined in this section. Safety data within the safety cutoff date but after last administration of study treatment will also be included. Only subjects who prematurely discontinue the study treatment will be included.

The number and percentage of subjects with at least one TEAEs that started after the date of last administration of study treatment will be reported by SOC, preferred term, and age group. The subset of subjects in the SAF who had data reported after the date of last administration of study treatment will be included in the analysis and the number of subjects in this subset will be the denominator in calculating the percentage.

Summary statistics for vital signs measurements and changes from baseline. These descriptive summaries will be presented by vital sign parameter, treatment group and visit-window.

Summary statistics for each ECG parameter and change from baseline. These descriptive summaries will be presented by vital sign parameter, treatment group and visit-window.

In addition, subjects with notable lab abnormalities or clinically notable vital signs will be listed.

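### SAP Table 2-7 and its text disagree on the first off-drug window, which reports the 2-month follow-up visit, and some values taken days after the last dose, as Month 3

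*SAP*

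**What the plan says.** SAP 2.1.2.2 covers data collected after the study drug stops. It presents Table 2-7 as the place "where the Start day and End day are relative to the date of last administration of study drug". The first row is the last assessment on drug, which means on or before the last dose date. The next row reads "Month 3 after LDD 2 90 135" (start, target and end day). Further rows follow in 90-day steps up to Month 27. The paragraph above the table defines that same Month 3 window as "assessments taken at least 1 day after but no more than 135 days after" the last administration.

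For the treatment period, SAP 2.1.2.1 builds windows around "the targeted visit date as defined in the evaluation schedule of the clinical study protocol" and requires them to have no gaps and no overlaps.

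Under Protocol Section 3, participants who complete treatment "will return for the Follow-up visit 2 months after the last dose of study drug". Protocol Section 8 adds: "In the study, one month is defined as 30 calendar days". Section 9.1.1 asks participants who stop treatment early to "return for the end of treatment (EOT) and follow up visits indicated" in Table 8-1, which schedules vital signs and ECG at EOT, at EOS and at follow-up.

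The windows feed SAP 2.8.6, which is limited to premature discontinuers and applies no safety cutoff. For vital signs, and in the same words for ECG, it says: "These descriptive summaries will be presented by vital sign parameter, treatment group and visit-window".

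**The concern.** There are three faults in one row.

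- The text and the table give different ranges for the same window, so a programmer has to guess which one governs.
- The post-treatment visit that the protocol names is at 2 months, yet the first off-drug row targets day 90. A visit made on time is shown under the wrong month.
- The row runs from the first days after the last dose to day 135. It therefore accepts an EOT value taken while the participant is still close to fully exposed, alongside values taken after washout.

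The off-drug summary is meant to show what happens once exposure ends. Protocol Section 1.1 says that the blood pressure rise on fingolimod reverses when therapy stops. A cell that mixes near-on-drug and washed-out values under one label is a poor place to look for that reversal.

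**Working it through.** **Inputs.** Table 2-7 rows and their text (SAP 2.1.2.2); post-discontinuation day as a plain date difference, without adding 1 (SAP Table 2-1); choice among several values in a window (SAP 2.1.2.3); 9-day half-life (SAP 2.1); 30-day month (Protocol Section 8); follow-up at study days 775 to 785 (Protocol Table 8-1).

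**Step 1: reproduce the table's end days.** Each end day should be the midpoint of adjacent targets: (90 + 180)/2 = 135, (180 + 270)/2 = 225, and so on to (720 + 810)/2 = 765. The last row ends at 810 + 45 = 855. All end days reproduce. The difficulty is confined to the first window.

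**Step 2: compare text and table.** The text covers 1 to 135 days after the last dose.

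| Numbering of the last dose date | Table days 2–135, as days after last dose | Days in the text but not in the table |
|---|---|---|
| Day 0 (plain difference, as in Table 2-1) | 2 to 135 | 1 |
| Day 1 | 1 to 134 | 135 |

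The two differ by exactly one day under either convention. Under the first, and going by the table alone, an assessment on the day after the last dose is neither the last assessment on drug nor in any later window.

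**Step 3: place the follow-up visit.** Nominally it is 2 × 30 = 60 days after the last dose. For a last dose on day 720, the range is 775 − 720 = 55 to 785 − 720 = 65 days. All of this lies in the Month 3 row, 90 − 65 = 25 to 90 − 55 = 35 days before its target.

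**Step 4: see which value represents Month 3.** Apply the rule of 2.1.2.3 (closest to target, the later one if tied) with target 90.

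| Assessments, days after last dose | Value chosen |
|---|---|
| 3 and 60 | 60 |
| 14 and 55 | 55 |
| 3, 60 and 88 | 88 |
| 3 only | 3 |

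An early value is used only when nothing closer to day 90 exists, for example when EOT was attended and follow-up was not.

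**Step 5: drug remaining.** The fraction is 2^(−d/9), with d in days after the last dose.

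| d | 2 | 3 | 7 | 14 | 30 | 60 | 90 |
|---|---|---|---|---|---|---|---|
| Remaining | 86% | 79% | 58% | 34% | 9.9% | 1.0% | 0.1% |

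All of these days fall in the single Month 3 row.

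**Step 6: a rough ceiling on the blood pressure effect.** Protocol Section 1.1 gives average rises of about 3 mmHg systolic and 2 mmHg diastolic. Assume that the whole rise is present in EOT-only values and fully gone in the others. If a share p of participants in the cell are EOT-only, the mean moves by about 3p and 2p mmHg. The documents do not give p. For p from 0.1 to 0.5, the shift is 0.3 to 1.5 mmHg systolic and 0.2 to 1.0 mmHg diastolic.

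**The case against.** The strongest reply is that the quarterly grid is deliberate. SAP 2.5.3 expects participants who stop treatment to stay in the study and follow the assessment schedule. SAP Table 2-1 ties the EOT visit to those who agree to do so, and 2.1.2.2 draws on data from both the treatment and follow-up periods. For such participants, 90-day steps after the last dose are sensible. This stands as a reason to keep the later rows. It also means that the 2-month visit cannot be called the only possible post-treatment visit. It does not give the 2-month visit a correct label, and Protocol 9.1.1 names only the EOT and follow-up visits for discontinuers.

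Second, the statement that windows surround scheduled visits belongs to the treatment-period section, whereas 2.1.2.2 anchors its windows on the last dose. That is fair. The point therefore rests on the label and target of the row, and on its contradiction with its own text, rather than on a breach of 2.1.2.1.

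Third, closest-to-target selection protects most cells (Step 4). This also stands, with one reservation: 2.1.2.3 words the rule for unscheduled assessments that replace a missed scheduled visit, so its use for two scheduled visits in one window is left to inference.

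A reader might go further and infer any of the following, which the documents do not support:

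- *That the 2-month visit has no window.* Day 60 lies inside days 2 to 135; only the label and target are wrong.
- *That data are lost.* The text of 2.1.2.2 includes the day after the last dose, and 2.1.2.3 puts all results in listings.
- *That next-day EOT visits are common.* Neither document gives their timing.
- *That about 20 of 100 participants are affected.* The 20% drop-out is a sample-size allowance, not a forecast of early treatment stops or of EOT-only attendance.
- *That the reversal of blood pressure will be hidden.* The percentages in Step 5 describe drug remaining, not effect, and the shift in Step 6 is small.

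**Conclusion.** The point holds as a minor error in the plan as written. Text and table contradict each other by one day under any numbering. The 2-month visit is reported under a label whose target is 25 to 35 days later. An EOT-only discontinuer can be summarised as Month 3 with more than half of the drug still present (58% at day 7). The reach is narrow: the descriptive vital-sign and ECG summaries of SAP 2.8.6, in premature discontinuers only. The primary ARR analysis and the safety tables with the 45-day cutoff do not use these windows.

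This rests on three assumptions: the 2-month interval that Section 3 states for completers also applies to discontinuers who attend follow-up, as the general visit description in Protocol Section 8 suggests; elimination is first-order with the SAP's 9-day half-life; and the selection rule of 2.1.2.3 is applied to scheduled visits. If that last assumption fails, the plan does not say which of two scheduled values enters the cell.

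**What to change.** In SAP 2.1.2.2, define the day as assessment date minus last dose date, and use day 1 as the start of the first off-drug window in both text and table. Replace the first off-drug row with three contiguous rows:

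| Window | Start | Target | End |
|---|---|---|---|
| Early post-drug / EOT | 1 | – | 30 |
| Month 2 after LDD | 31 | 60 | 75 |
| Month 3 after LDD | 76 | 90 | 135 |

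The boundaries follow the table's own midpoint logic: (0 + 60)/2 = 30 and (60 + 90)/2 = 75. The follow-up visit at days 55 to 65 then falls in Month 2, and no day up to 135 is left without a window. Keep the later quarterly rows for discontinuers who continue the visit schedule. Add a sentence to 2.1.2.3 saying that closest-to-target selection also applies when two scheduled visits fall in one window, and state how one value is chosen in the early row, which has no target.

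The cost is a table and text edit and a change to one derivation, best made before database lock, with no new data. The drawback is fewer participants per window in a group that is already a subset.
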